# C.3 Randomization and drug dispensation:

Patients who consent will be stratified by age (40-60 and 61-80) and disease severity (H&Y 1-2.5, 3-5) and divided into blocks of a few patients each, depending on order of recruitment. Equal numbers from each block will be assigned to CBD or placebo group in random order.

[name], the PI, will obtain an amended DEA Schedule 1 license prior to the shipment of the study drug and all procedures of drug handling will be according to DEA specifications and protocol provided by University of Mississippi researchers. Briefly, designated study personnel will receive the study drug, do the formulation procedure, store it, measure and label it. The PI or PharmDs will dispense to the participant.

## C.4 Blinding assessment and Un-blinding procedures:

#### **Blinding assessment:**

Active drug and placebo will look and taste the same as much as possible. Participants and all study personnel except for [name], [name], and her fellow, are blinded.

At the end of treatment phase visits, participants will be asked about the treatment allocation they think they were assigned. The answers are taken in forms with five responses of "strongly believe the treatment is drug," "Somewhat believe the treatment is drug." "Somewhat believe the treatment is drug." "Somewhat believe the treatment is placebo," "Strongly believe the treatment is placebo," and "Don't know."

# **Un-blinding procedures:**

The identity of the treatment assigned to individual participants can be revealed in an emergency only. The PI is responsible for ensuring that the instructions on how to request un-blinding of treatment are stored safely, that their location is known, and that access is readily available to the relevant staff in case of an emergency. [name], the statistician will provide the information when un-blinding is requested by the PI. As a back-up, [name] will provide a file of sealed envelopes to the PI, which is kept in a locked file in her office. The location is known to the PI, sub-I, and coordinator. A sealed envelope coded with each participant number is provided. In the event that [name] is not available to provide break the blind the PI and designated staff can do so. A participant's treatment assignment should only be un-blinded when knowledge of the treatment is essential for the safety of the participant. Un-blinding for any other reason will be considered a protocol deviation.

#### **C.5 Stopping rules:**

Note there are no interim analyses planned.

#### **Participant stopping rules:**

- If participant cannot tolerate the study drug at any dose level
- if participant develops a CTCAE criteria grade 3 or 4 adverse event per that the Investigator determines is related the study drug
- Pregnancy or breast-feeding
- Requested by participant to terminate treatment
- Failure by the participant to attend consecutive study visits
- Participant is at significant risk of failing to comply with the provisions of the protocol as to cause harm to self or seriously interfere with the validity of the study results
- At the discretion of the IRB, Food and Drug Administration (FDA)

If a participant is withdrawn from the study, all efforts will be made to complete the early termination visit that includes efficacy assessments and safety follow-up. In addition, women of childbearing potential will have a post-study pregnancy test performed at the early termination visit.

Withdrawals and the reason for withdrawal will be tabulated by treatment group. The number and percentage of participants who complete the study will be summarized by treatment group. The number and percentage of participants who withdraw from the study will be tabulated by original treatment group and last treatment taken at time of withdrawal. Study medication discontinuations will be summarized in a similar fashion.

Participants will be advised that they are free to withdraw from the study at any time. Reasons that participants may be withdrawn from the study include the following:

Participant discontinued study medication and wishes to withdraw.

Participant consent is withdrawn.

# **Study stopping rules**

- Participants are unable to be recruited
- Study drug becomes unavailable
- Participants are unable to tolerate the study drug at any dose level
- Discovery (from this or other studies) of an unexpected, serious, or unacceptable health hazard to participants, i.e., development of the same adverse event, CTCAE criteria grade ≥3, related to study drug in ≥2 participants
- At the discretion of the IRB, Food and Drug Administration (FDA).

# C.6 Adverse events assessments:

Adverse events will be classified according to the grades defined in the Common Terminology Criteria for Adverse Events (CTCAE). Any adverse event or abnormal laboratory test value that is serious (see definition below) and occurs after administration of the investigational product will be documented by the Sponsor-Investigator within 24 hours of discovery of the event. Severity of Adverse Events

The severity of each AE/SAE will be classified into one of five defined grades. The CTCAE displays Grades 1 through 5 with unique clinical descriptions of severity for each AE based on this general guideline:

Grade 1: Mild; asymptomatic or mild symptoms; clinical or diagnostic observations only; intervention not indicated.

Grade 2: Moderate; minimal, local, or noninvasive intervention indicated; limiting age-appropriate instrumental ADLs. Instrumental ADLs refer to preparing meals, shopping for groceries or clothes, using the telephone, managing money, etc.

Grade 3: Severe or medically significant but not immediately life-threatening; hospitalization or prolongation of hospitalization indicated; disabling; limiting self-care ADLs. Self-care ADLs refer to bathing, dressing and undressing, feeding self, using the toilet, taking medications, and not bedridden.

Grade 4: Life-threatening consequences; urgent intervention indicated.

Grade 5: Death related to AE.

The severity of the AE will be recorded in the appropriate section on the AE page of the CRF. Serious Adverse Events (SAEs)

The evaluation of severity will be distinguished from the evaluation of "seriousness." A severe event might not meet the criteria for seriousness and a serious event might be evaluated as mild or moderate. For example, a participant might have a severe headache that does not require hospitalization and is consequently not serious; or a participant might have a mild myocardial infarction that requires hospitalization and is therefore serious.

An SAE is any untoward medical occurrence at any dose that:

- Results in death during the period of protocol-defined surveillance. Death due to PD will not be considered an SAE. However, if a patient requires hospitalization due to an AE related to PD, the specific sign or symptom leading to hospitalization will be reported as an SAE. If death due to PD occurs outside of hospitalization and is considered to be due solely to the patient's PD, no SAE report is required. The death will be recorded as part of PD and patient disposition.
- Is life-threatening (NOTE: The term "life-threatening" in the definition of "serious" refers to an event in which the participant, in the view of the Investigator, is at risk of death at the time of the event; it does not refer to an event that hypothetically might cause death if it was more severe).
- Requires inpatient hospitalization or prolongation of existing hospitalization\*.
- Results in persistent or significant disability or incapacity.
- Results in a congenital anomaly/birth defect.

\*Hospitalization: Outpatient treatment in an emergency room is not in itself an SAE, although the reasons for it might be (e.g., bronchospasm, laryngeal edema). Hospital admission and/or surgical operations planned before or during a study are not considered SAEs if the illness or disease existed before the participant was enrolled in the study, provided that it did not deteriorate in an unexpected way during the study. It should be noted that for this study, participants with planned or anticipated surgery should not be enrolled into the study.

Important Medical Events: Medical and scientific judgment will be exercised in deciding whether a case is serious in situations where important medical events may not be immediately life-threatening or result in death, hospitalization, disability, or incapacity but may jeopardize the participant or may require medical or surgical intervention to prevent one or more outcomes listed in the definition of serious. These should usually be considered as serious, and examples of such events are:

- Angioedema not severe enough to require intubation but requiring intravenous hydrocortisone treatment
- Hepatotoxicity caused by paracetamol (acetaminophen) overdose requiring treatment with N-acetylcysteine
- Intensive treatment in an emergency room or at home for allergic bronchospasm
- Development of drug dependency or drug abuse.

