#### Literature review of safety and tolerability of CBD

There are more than 30 reported human trials testing CBD, but doses, cannabinoid compositions, and results vary widely. Generally, the studies find CBD is well tolerated. Several studies suggest that CBD does not affect food intake, affect physiological parameters (heart rate, blood pressure and body temperature), affect gastrointestinal transit, or alter psychomotor or psychological functions [Zuardi AW, et al. 2009; Riedel G, et al. 2009; Scopinho AA, et al. 2011; Gomes FV, et al. 2013; Bergamaschi MM, et al. 2011; Bhattacharyya S, et al. 2010]. Also, chronic use and high doses up to 1,500 mg/day of CBD are reportedly well tolerated in humans [Zuardi AW, et al. 1995]. Conversely, some studies reported that this cannabinoid has adverse effects, including inhibition of hepatic drug metabolism, alterations of in vitro cell viability, and decreased fertilization capacity [Bergamaschi MM, et al. 2011; Bornheim LM, et al. 1994; Narimatsu S, et al. 1990],

Extensive reports of CBD administration across a wide range of concentrations did not detect important adverse or toxic effects [Bergamaschi MM, et al. 2011]. With a median Lethal Dose (LD50) of 212 mg/kg in rhesus monkeys, CBD has a low toxicity [Rosenkrantz H, et al. 1981]. Some studies investigated mutagenic or teratogenic effects and describe no such events [Matsuyama SS, Fu TK. 1981; Dalterio S, et al. 1984]. We reviewed the tolerability of CBD doses used in human studies to date – one study suggested over 300 mg per day may exacerbate bradykinesia [Consroe P, et al. 1986], but other studies used 7.5 to 1500 mg per day without significant adverse effects [Bergamaschi MM, et al. 2011; Zuardi AW, et al. 1995]. Most studies used doses in the range of 200 - 600 mg/day.

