CBD is highly protein bound, so rasagiline, selegiline, and rotigotine levels may increase transiently. Checking plasma concentration levels of these anti-PD medications is not a routine clinical practice. Thus the PI will monitor participants on these medications for clinical changes. The most important and likely adverse effects of a clinically significant increase in the level of selegiline is anxiety, dyskinesia, agitation, insomnia, and hallucinations. The most important and likely adverse effects of a clinically of rasagiline, ropinirole, and selegiline is an increase in the motor symptoms of Parkinson disease, which are resting tremor, bradykinesia, rigidity, and postural instability. The most important and likely adverse effects of a clinically significant increase in rotigotine is low blood pressure, somnolence, and impulse control disorders. Instructions to Participants at the End of Each Stage:

We will provide the following instructions about continued marijuana use at the end of the study to facilitate safety:

Cannabis (marijuana) is composed of many substances. Street cannabis is high in tetrahydrocannabinol (THC), which causes the "high" feeling. Street cannabis has lower concentrations of cannabidiol (CBD). The cannabis preparations sold at dispensaries have various concentrations of THC and CBD. The ratio of THC to CBD plays a role in a preparation's beneficial and adverse effects. Studies to date suggest that THC is especially risky in person with PD, because it may worsen thinking and coordination and cause psychiatric symptoms. The precise effects of all the substances in cannabis is unknown. Using marijuana should be under the supervision of your physician, with monitoring the symptoms of PD and other diseases, as well as the interactions of marijuana and other drugs you take.

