### C.7 Risks of Study Drug:

A review of 25 studies on the safety and efficacy of CBD did not identify significant side effects across a wide range of dosages, including acute and chronic dose regimens, using various modes of administration [Bergamaschi M.M., et al. 2011]. There are no rare but serious side effects reported. The most frequently occurring side effect was somnolence (i.e.drowsiness) (25%). Other side effects, in order of prevalence, include: diarrhea (19%), decreased appetite (19%), fatigue (13%), convulsion (11%), increased appetite (9%), status epilepticus (8%), lethargy (7%), weight increased (7%), and weight loss (6%) [Devinsky O, et al. 2016]. Other side effects include extrapyramidal symptoms, increased prolactin levels, weight gain, increased serum concentrations of antiepileptic drugs, and elevated liver function tests.

Table 6 and 7 show the adverse reactions of pure CBD, i.e., Epidiolex®.

**Table 6.** Adverse events and treatment-emergent serious adverse events of purified CBD reported in pediatric treatment-resistant epilepsy (an open-label interventional trial, maximum dose 25-50 mg/kg/day of CBD) [Devinsky O, et al. 2016]

ing/kg/day of CDD) [Devinsky 0, et al. 2010]	
Adverse events (reported >5% of patients)	N =162
Somnolence	41 (25%)
Decreased appetite	31 (19%)
Diarrhoea	31 (19%)
Fatigue	21 (13%)
Convulsion	18 (11%)
Increased appetite	14 (9%)
Status epilepticus	13 (8%)
Lethargy	12 (7%)
Weight increased	12 (7%)
Weight decreased	10 (6%)
Drug concentration increased	9 (6%)
Treatment-emergent serious adverse events	
Status epilepticus	9 (6%)
Diarrhoea	3 (2%)
Weight decreased	2 (%)
Convulsion	1 (<1%)
Decreased appetite	1 (<1%)
Drug concentration increased	1 (<1%)
Hepatotoxicity	1 (<1%)
Hyperammonaemia	1 (<1%)
Lethargy	1 (<1%)
Unspecified pneumonia	1 (<1%)
Aspiration pneumonia	1 (<1%)
Bacterial pneumonia	1 (<1%)
Thrombocytopenia	1 (<1%)

**Table 7.** Adverse events occurring with a frequency of greater than 10% in either trial group (RCT in 120 children and young adults with the Dravet syndrome and drug-resistant seizures, 20 mg/kg/day of CBD) [Devinsky O, et al. 2017]

System Organ Class and Preferred Term	Cannabidiol (n=61)	Placebo (n=59)
Gastrointestinal		
Diarrhea	19 (31%)	6 (10%)
Vomiting	9 (15%)	3 (5%)
General		
Fatigue	12 (20%)	2 (3%)
Pyrexia	9 (15%)	5 (8%)
Infections: upper respiratory tract infection	7 (11%)	5 (8%)
Metabolism: decreased appetite	17 (28%)	3 (5%)
Nervous system		
Convulsion	7 (11%)	3 (5%)

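### The SAE definition exempts deaths attributed to Parkinson disease, in two sentences that do not agree, and no planned safety comparison would count such a death

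*Combined protocol and SAP*

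**What the plan says.** The rule is in Section IV.C.6, under Serious Adverse Events. The first bullet makes any event that results in death an SAE, and then qualifies this in four steps:

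- The exclusion carries no condition: "Death due to PD will not be considered an SAE".
- For an admission caused by a PD-related event, "the specific sign or symptom leading to hospitalization will be reported as an SAE".
- The report itself is waived under two conditions. One is the place of death ("If death due to PD occurs outside of hospitalization"); the other is a judgement that PD was its only cause.
- The exempt death goes elsewhere: "The death will be recorded as part of PD and patient disposition".

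The same section requires serious events after dosing to be documented within 24 hours of discovery. It leaves the causality judgement to the Investigator.

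On whether the drug might worsen parkinsonism, Section IV.C.7 says "Other side effects include extrapyramidal symptoms". Section IV.C.2 expects that levels of rasagiline, ropinirole and selegiline may fall, and describes the important clinical effect this way: it "is an increase in the motor symptoms of Parkinson disease, which are resting tremor, bradykinesia, rigidity, and postural instability". (Words are missing from the start of that sentence; it is read here with the paragraph on falling levels.)

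For analysis, outcome 1.1 in Section IV.A and the first safety item in Section IV.F compare the frequency of study-related adverse events between arms. Section IV.C.5 tabulates withdrawals and their reasons by treatment group.

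**The concern.** Calling a death due to PD presumes that the drug did not worsen PD, yet the drug's effect on PD motor signs is the trial's primary question. Parkinsonism made worse by the drug, or by its effect on other anti-PD medication, can look like the disease. This is therefore where a single investigator's attribution is least secure, and the documents describe no independent adjudication of deaths.

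The attribution settles whether the death gets SAE documentation. It would also keep the death out of the between-arm event comparison, because a death ascribed to PD will ordinarily be judged not study-related. Safety and tolerability are the first secondary outcome, and a placebo arm can inform on excess deaths only if deaths are counted in both arms whatever their supposed cause. Death is not an efficacy endpoint, and the plan gives no reason for the exemption.

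**Working it through.** No stated figure is in dispute, so the check sets the rules side by side and then sizes the issue.

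**1. The two sentences.**

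| Death attributed to PD | Exclusion sentence | Waiver sentence |
|---|---|---|
| Outside hospital, PD judged the sole cause | Not an SAE | No report required |
| Outside hospital, PD plus another contributor | Not an SAE, if still called due to PD | Waiver does not apply |
| In hospital | Not an SAE | Waiver does not apply; the sign or symptom that led to a PD-related admission is an SAE, but the sentence is silent on the death |

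They agree only in the first row. Section IV.C.6 also defines CTCAE grade 5 as death related to an adverse event, and does not say how that grade fits with the exemption.

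**2. Where a PD-attributed death would and would not appear.**

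- SAE documentation within 24 hours: no, because the rule applies to serious events.
- Study-related event comparison (IV.A 1.1, IV.F): no. Under IV.C.6 an event is not related if a clearly likelier alternative exists, and the natural history of underlying disease is one of the alternatives weighed.
- Other safety analyses in IV.F: no. They cover vital signs, examination, EKG, laboratory tests, rating scales and drop-out for drug intolerance. None compares all-cause deaths.
- PD and disposition record: yes, and possibly the by-arm withdrawal tables of IV.C.5.
- FDA 7-day report: this needs a fatal or life-threatening event that is unexpected and possibly related. Relatedness decides it.
- Numerical study-stopping trigger: this needs the same grade 3 or higher event, related to study drug, in at least 2 participants. Relatedness decides it.

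**3. How many deaths might be affected.** The documents give no mortality rate. Assume annual all-cause mortality r between 1% and 10%, 75 participants, and 28 days from first dose to the safety visit. The risk per person is p = 1 − (1 − r)^(28/365.25). Expected deaths are 75p, and the chance of at least one is 1 − (1 − p)^75.

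| r (assumed) | Expected deaths | Chance of at least one |
|---|---|---|
| 1% | 0.06 | 6% |
| 3% | 0.17 | 16% |
| 5% | 0.29 | 26% |
| 10% | 0.60 | 45% |

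These are deaths from any cause. Those attributed to PD can only be fewer.

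**4. What one death weighs.** In an arm of 30 (planned completers), one death is 1/30 = 3.3%, exact 95% interval 0.08% to 17.2%. With no deaths the upper limit is 11.6%. In an arm of 37 (75/2, rounded down), one death is 1/37 = 2.7%, interval 0.07% to 14.2%; with none, the upper limit is 9.5%.

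**The case against.** The case for leaving the text alone has several sound parts.

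- **The waiver is narrow.** A death that the Investigator sees as partly drug-caused is not solely due to PD, so the waiver does not cover it. A PD-related admission produces an SAE for the symptom behind it, and a life-threatening worsening meets a separate SAE criterion. This stands: the harm needs a misattribution as well as the exemption. It does not rescue the exclusion sentence, which has no such limits.
- **The death is not hidden.** A reader might infer that it would vanish from the trial. The text does not support that, since the death is recorded in disposition and may show in the withdrawal tables. It is missing from SAE documentation and from the safety comparison.
- **Expedited reporting and stopping.** A reader might infer that the exemption disables the 7-day report and the stopping trigger. It does not by itself. Both depend on relatedness, and a death judged unrelated would set off neither even if it were an SAE.
- **Bradykinesia.** It is tempting to cite the background statement that "one study suggested over 300 mg per day may exacerbate bradykinesia". The target here is 2.5 mg/kg/day, or 2.5 × 84 = 210 mg/day for the protocol's average participant. Passing 300 mg/day needs a weight above 300/2.5 = 120 kg. The same sentence reports other studies at 7.5 to 1500 mg/day without significant adverse effects. The point does not rest on it.
- **Randomisation does not replace attribution.** The intervals above are far too wide for an arm comparison to settle the cause of one death, and expedited reporting still needs a causality judgement. That favours recording attribution alongside the event rather than using it to decide whether the event counts as serious.

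**Conclusion.** The point holds as a gap in safety reporting. The exclusion and waiver sentences in IV.C.6 are inconsistent, and together they let an attribution to PD remove a death from SAE documentation. Section IV.F has no analysis that would bring that death back into the comparison between arms.

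The practical weight is modest. Treatment lasts about two weeks and follow-up from first dose about four, so few or no deaths are expected. The expected counts rest on an assumed mortality range, not on the documents. A reader might also infer that an SAE table would show zero deaths instead of one, but the plan defines no SAE table. The supportable statement is that no planned safety comparison would include the death. The conclusion also assumes that disposition records are not otherwise fed into the safety analysis; nothing in the documents says that they are.

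**What to change.** 1. In Section IV.C.6, delete the exclusion of PD deaths, the waiver of the report, and the sentence sending such deaths to the PD and disposition record alone. Keeping the exemption would still require reconciling the first two with each other and with CTCAE grade 5.
2. State that every death from first dose to last study visit is documented as an SAE under the existing 24-hour rule, with attribution to PD recorded in a separate field.
3. In Section IV.F, add a descriptive by-arm tabulation of all deaths and all SAEs, regardless of attribution.

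Steps 2 and 3 are both needed. Redefining the SAE alone would not bring a death judged unrelated into a comparison limited to study-related events. The cost is a few sentences, one field, one table, and at most one or two extra reports. Treatment and visits do not change.
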